10.2.2 Phase 2 Portion

The subject will receive treatment in repeated 28-day cycles of azacitidine (75 mg/m² SC or IV for 7 consecutive days or 5 days on/2 days off/2 days on) and/or blinded study medication (vadastuximab talirine or placebo; [Section 9.5.1](#)). In addition, procedures will be performed as indicated below.

10.2.2.1 Cycle 1

- Day 1, pretreatment:
 - Biomarker assessments ([Section 11.4](#))
 - Whole blood (sCD33 - cytokines and research; MDSC; CD33 expression; and PBMCs)
 - ECOG performance status and weight ([Section 11.5](#))
 - Clinical laboratory tests (CBC with differential and serum chemistry including ferritin; [Section 11.7](#))
 - PRO questionnaire ([Section 11.9](#))
 - Blood samples for ATAs (within 24 hours before beginning the azacitidine infusion; [Section 11.8](#))
- Days 1 to 6 (if azacitidine is administered on 7 consecutive days) or Days 1 to 5, and 8 (if administered 5 days on/2 days off/2 days on): Administer azacitidine according to the selected treatment schedule ([Section 9.5.1.3](#))
- Day 7 (if azacitidine is administered on 7 consecutive days) or Day 9 (if administered 5 days on/2 days off/2 days on), pretreatment:
 - PK sample collection (within 8 hours before beginning the blinded study medication) ([Section 11.4.1](#))
 - Biomarker assessments ([Section 11.4](#))
 - Whole blood (sCD33 - cytokines and research; MDSC; CD33 expression; and PBMCs)
 - Vital signs
 - After completion of pretreatment procedures, administer azacitidine ([Section 9.5.1.3](#)) followed by blinded study medication ([Section 9.5.1.2](#))
 - Vital signs (within 30 minutes after completing the blinded study medication infusion)
 - PK sample collection (within 15 minutes after completing the blinded study medication infusion; [Section 11.4.1](#))
- Day 15 (± 1 day):

- Clinical laboratory tests (CBC with differential, serum chemistry including ferritin, and urinalysis; [Section 11.7](#))

10.2.2.2 Cycle 2

- Day 1 (± 1 day), pretreatment:
 - ECOG performance status and weight ([Section 11.5](#))
 - PRO questionnaire ([Section 11.9](#))
 - Clinical laboratory tests (CBC with differential, serum chemistry including ferritin, and urinalysis; [Section 11.7](#))
 - Serology laboratory tests (inflammatory serologies; [Section 11.7](#))
 - Blood samples for ATAs (within 24 hours before beginning the azacitidine infusion; [Section 11.8](#))
- Days 1 to 6 (if azacitidine is administered on 7 consecutive days) or Days 1 to 5, and 8 (if administered 5 days on/2 days off/2 days on): Administer azacitidine according to the selected treatment schedule ([Section 9.5.1.3](#))
- Day 7 (if azacitidine is administered on 7 consecutive days) or Day 9 (if administered 5 days on/2 days off/2 days on), pretreatment:
 - PK sample collection (within 8 hours before beginning the blinded study medication infusion; [Section 11.4.1](#))
 - Whole blood (sCD33 - cytokines and research; MDSC; CD33 expression; and PBMCs)
 - Vital signs
 - After completion of pretreatment procedures, administer azacitidine ([Section 9.5.1.3](#)) followed by blinded study medication ([Section 9.5.1.2](#))
 - Vital signs (within 30 minutes after completing the blinded study medication infusion)
 - PK sample collection (within 15 minutes after completing the blinded study medication infusion; [Section 11.4.1](#))
- Day 15 (± 1 day):
 - Clinical laboratory tests (CBC with differential, serum chemistry including ferritin, and urinalysis; [Section 11.7](#))

- Day 22 to 29:
 - Clinical laboratory tests (CBC with differential; [Section 11.7](#))
 - Bone marrow examination ([Section 11.3](#))
 - Biomarker assessments ([Section 11.4](#))
 - Bone marrow (MDSC, CD33 expression, and mutation profiling)

10.2.2.3 Cycle 3

- Day 1 (± 1 day), pretreatment:
 - ECOG performance status and weight ([Section 11.5](#))
 - Clinical laboratory tests (CBC with differential and serum chemistry including ferritin; [Section 11.7](#))
 - Blood samples for ATAs (within 24 hours before beginning the azacitidine infusion; [Section 11.8](#))
- Days 1 to 6 (if azacitidine is administered on 7 consecutive days) or Days 1 to 5, and 8 (if administered 5 days on/2 days off/2 days on): Administer azacitidine according to the selected treatment schedule ([Section 9.5.1.3](#))
- Day 7 (if azacitidine is administered on 7 consecutive days) or Day 9 (if administered 5 days on/2 days off/2 days on), pretreatment:
 - Vital signs
- Day 7 (if azacitidine is administered on 7 consecutive days) or Day 9 (if administered 5 days on/2 days off/2 days on), posttreatment:
 - Administer azacitidine ([Section 9.5.1.3](#)) followed by blinded study medication ([Section 9.5.1.2](#))
 - Vital signs (within 30 minutes after completing the blinded study medication infusion)
 - PK sample collection (within 15 minutes after completing the blinded study medication infusion; [Section 11.4.1](#))
- Day 15 (± 1 day):
 - Clinical laboratory tests (CBC with differential, serum chemistry including ferritin, and urinalysis; [Section 11.7](#))

10.2.2.4 Cycles \geq 4

- Day 1 (\pm 1 day), pretreatment:
 - ECOG performance status and weight (Section 11.5)
 - Even-numbered cycles only: PRO questionnaire (Section 11.9)
 - Clinical laboratory tests (Section 11.7)
 - All cycles: CBC with differential and serum chemistry including ferritin
 - Even-numbered cycles only: urinalysis
 - Even-numbered cycles until CR, then every 4 cycles: Biomarker assessments (Section 11.4)
 - Whole blood (sCD33 - cytokines and research; MDSC; CD33 expression; and PBMCs)
 - Cycle 4 only: Serology laboratory tests (inflammatory serologies and special autoimmune serologies; Section 11.7)
 - Cycle 4, then every 4 cycles: Blood samples for ATAs (within 24 hours before beginning the azacitidine infusion; Section 11.8)
- Days 1 to 6 (if azacitidine is administered on 7 consecutive days) or Days 1 to 5, and 8 (if administered 5 days on/2 days off/2 days on): Administer azacitidine according to the selected treatment schedule (Section 9.5.1.3)
- Day 7 (if azacitidine is administered on 7 consecutive days) or Day 9 (if administered 5 days on/2 days off/2 days on), pretreatment:
 - Vital signs
- Day 7 (if azacitidine is administered on 7 consecutive days) or Day 9 (if administered 5 days on/2 days off/2 days on), posttreatment:
 - Administer azacitidine (Section 9.5.1.3) followed by blinded study medication (Section 9.5.1.2)
 - Vital signs (within 30 minutes after completing the blinded study medication infusion)
 - Cycle 4, then every 4 cycles: PK sample collection (within 15 minutes after completing the blinded study medication infusion; Section 11.4.1)

- Day 15 (± 1 day):
 - Cycle 4 only: Clinical laboratory tests (CBC with differential, serum chemistry including ferritin, and urinalysis; [Section 11.7](#))
- Day 22 to 29: Even-numbered cycles until CR, then every 4 cycles:
 - Clinical laboratory tests (CBC with differential; [Section 11.7](#))
 - Biomarker assessments ([Section 11.4](#))
 - Bone marrow (MDSC and CD33 expression)
 - Bone marrow examination ([Section 11.3](#))

Any AEs ([Section 12.1](#)) and SAEs ([Section 12.1.1](#)), reported or observed, will be reported on the eCRF, and SAEs will be reported as indicated in [Section 12.1.5](#). Any changes in concomitant medications will be recorded at each visit or as they are reported.

10.3 End of Treatment

For all subjects in both portions of the study, an EOT visit will be performed 30 to 37 days after the last dose of study treatment (vadastuximab talirine or placebo and/or azacitidine). At the EOT visit, the following assessments/procedures will be performed:

- Physical examination and ECOG performance status ([Section 11.5](#))
- Serum or urine pregnancy test (women of childbearing potential only)
- Clinical laboratory tests (CBC with differential, serum chemistry including ferritin, urinalysis; [Section 11.7](#))
- Serology laboratory tests (inflammatory serologies and special autoimmune serologies; [Section 11.7](#))
- PRO questionnaire ([Section 11.9](#))
- Bone marrow examination ([Section 11.3](#))
- Blood samples for ATAs ([Section 11.8](#))
- Biomarker assessments ([Section 11.4](#))
 - Whole blood (sCD33 - cytokines and research; MDSC; CD33 expression; and PBMCs)
 - Bone marrow (MDSC; CD33 expression; and mutation profiling) – not required if a sample was collected within the previous 4 weeks

Any AEs (Section 12.1) and SAEs (Section 12.1.1), reported or observed, will be reported on the eCRF, and SAEs will be reported as indicated in Section 12.1.5. End-of-treatment evaluations should be obtained before the initiation of non-protocol therapy. If the EOT visit occurs less than 30 days after the last treatment with any study treatment, the subject will be contacted by telephone 30 to 37 days after the last study treatment to assess any AEs or changes in concomitant medications that may have occurred since the EOT visit.

10.4 Follow-Up

If study treatment is discontinued prior to disease progression or relapse, bone marrow samples will be obtained from assessments conducted every 4 months through 24 months after EOT or until initiation of another anticancer treatment, progression, or relapse.

Events of sinusoidal obstruction syndrome/veno-occlusive disease (SOS/VOD) that occur within 180 days of the last dose of vadastuximab talirine or blinded study drug will be reported to the Sponsor, regardless of causality. Patients who undergo subsequent allo-SCT within 180 days of the last dose of vadastuximab talirine or blinded study drug in the absence of relapse and additional therapy will be followed for SOS/VOD for 100 days post-transplant.

Subjects will be contacted for survival information and collection of subsequent anticancer treatment information approximately every 2 months until death or study completion.

If subjects become candidates for stem cell transplant after enrollment, initiation of preparative regimen for stem cell transplant should not be performed until at least 30 days after the last dose of vadastuximab talirine. It is recommended to avoid transplant conditioning regimens with higher risk of SOS/VOD, including total-body irradiation and multiple alkylating agents. [27, 28] An association of SOS/VOD in patients with pre-exposure to vadastuximab talirine has not been established.

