- b For subjects who discontinue without having experienced disease progression follow-up will include disease assessment (CBC and bone marrow) every 4 months for 24 months or until disease progression. Subjects will be followed every 2 months for survival until death or the end of the study.

Unblinding a subject's treatment assignment will be limited to emergency circumstances where knowledge of the treatment assignment would affect decisions regarding the management of the subject. In the event of such an emergency circumstance, a formal unblinding procedure will be followed to allow the Investigator to immediately access a

subject's treatment assignment. Information on study treatment assignment should not be distributed to any other personnel involved in the clinical trial.

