- p Bone marrow examination should be based on a bone marrow biopsy; however, if marrow cannot be biopsied, but aspiration is successful, the aspirate may be used to determine blast count. For subjects requiring a marrow evaluation to assess cellularity due to cytopenias, a biopsy is required.
- q Only required if not conducted within 4 weeks prior to EOT.
- r If study treatment discontinued prior to disease progression or relapse, obtain every 4 months through 24 months after EOT or until initiation of another anticancer treatment, progression, or relapse.
- s Contact subject for survival status every 2 months after EOT until death or study closure. Collection of subsequent anticancer treatment information.
- t See [Sections 10.4](#) and [12.1.4](#) for follow-up of adverse events of special interest.
- u Before and within 30 minutes after vadastuximab talirine (Phase 1 Portion), or blinded study drug (Phase 2 Portion) administration.

Table 5: Schedule of Pharmacokinetic, Immunogenicity, and Biomarker Assessments – Phase 1 Portion

Cycle	Day	Time	Window	Whole Blood						Bone Marrow Aspirate			
				PK	ATA	PNH & HLA-DR15	sCD33, Cytokines & Research	MDSC	CD33 Expression	PBMC	MDSC	CD33 Expression	Mutation Profiling
Baseline/Screening			Within 28 d prior to study drug			X					X ^e	X ^e	X ^e
			Within 7 d prior to study drug							X			
1	1	Pre-azacitidine	within 24 hr		X		X	X	X				
	7 or 9	Pre-vadastuximab talirine	within 24 hr	X			X	X	X		X ⁱ	X ⁱ	
		End of vadastuximab talirine administration	within 15 min postdose	X									
		2 hr	± 15 min	X									
		6 hr	± 2 hr	X									
	8 ^b	24 hr	± 4 hr	X									
	10 ^c	72 hr	± 4 hr	X				X	X				
	15 ^d	192 hr	± 4 hr					X	X				
28		Day 22-29											
2	1	Pre-azacitidine dose	within 24 hr		X		X	X	X	X			
	7 or 9 ^a	Pre-vadastuximab talirine	within 8 hr	X									
		End of vadastuximab talirine administration	within 15 min postdose	X									
		2 hr	± 15 min	X									
	8 ^b	24 hr	± 4 hr	X									
	10 ^c	72 hr	± 4 hr	X									
28		Day 22-29								X ^e	X ^e		
3	1	Pre-azacitidine	within 24 hr		X								
	7 or 9 ^a	End of vadastuximab talirine administration	within 15 min postdose	X									
4+	1	Pre-azacitidine	within 24 hr		X ^h		X ^f	X ^f	X ^f	X ^f			
	7 or 9 ^a	End of vadastuximab talirine administration	within 15 min postdose	X ^h									
	28		Day 22-29								X ^{e,f}	X ^{e,f}	
End of treatment			30–37 d post last dose		X		X	X	X	X	X ^{e,g}	X ^{e,g}	X ^{e,g}

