13.6.4.2 Secondary Efficacy Endpoints

Time-to-event variables (DOR, PFS, and OS) will be summarized descriptively using the Kaplan-Meier estimate. Additional details will be provided in the SAP. Secondary endpoints will be assessed in the ITT population (except as indicated below).

CR Rate: Response (CR/Marrow CR, PR, ORR [CR/Marrow CR+PR], HI rate, stable disease [SD], and PD) will be summarized descriptively by treatment arm. CR rate will be summarized with 90% confidence intervals. Rate of transformation to AML will also be summarized.

DOR (for PR/CR and CR): DOR is defined as the time from first observation of response (PR+CR/Marrow CR or CR/Marrow CR) to disease progression/relapse or death from any cause, whichever occurs first. Durations will be assessed in the ITT population with a PR or CR and calculated separately for subjects with CR/Marrow CR and those with PR+CR/Marrow CR combined. For subjects with a remission without subsequent disease progression/relapse or death on study, DOR will be censored at the time of the last disease assessment demonstrating a lack of disease progression/relapse. Subjects who receive another anti-neoplastic therapy in the absence of documented progression will be censored at the time of receiving off-protocol therapy for

malignancy, EXCEPT that subjects who receive stem cell transplant in remission will continue to be followed for progression.

Progression-free Survival: PFS is defined as the time from first dose of study medication to first documentation of disease progression/relapse, or to death due to any cause, whichever occurs first. For subjects without disease progression/relapse or death on study, PFS will be censored at the time of the last on-study disease assessment demonstrating a lack of disease progression/relapse. If more than one date of progression is available, the earliest date will be used to determine PFS. Subjects who receive another anti-neoplastic therapy in the absence of documented progression will be censored at the time of receiving off-protocol therapy for malignancy, EXCEPT that subjects who receive stem cell transplant in remission will continue to be followed for progression.

Overall Survival: OS is defined as the time from first dose of study medication to death due to any cause. For subjects not known to have died at the end of the study, OS will be censored at the time the subject was last known to be alive (including follow-up data).

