**Progression-Free Survival:** PFS is defined as the time from first dose of study medication to first documentation of disease progression/relapse, or to death due to any cause, whichever occurs first. For subjects without disease progression/relapse or death on study, PFS will be censored at the time of the last on-study disease assessment demonstrating a lack of disease progression/relapse. If more than one date of progression is available, the earliest date will be used to determine PFS. Subjects who receive another antineoplastic therapy in the absence of documented progression will be censored at the time of receiving off-protocol therapy for

malignancy, EXCEPT that subjects who receive stem cell transplant in remission will continue to be followed for progression.

**Relative Dose Intensity (RDI):** is defined as the absolute dose intensity over the intended dose intensity,

$$\text{RDI} = \text{ADI} / \text{IDI} * 100.$$

Where IDI (intended dose intensity) is defined as the intended dose of drug (mg/kg) per unit of time.

**Study Drug:** The study drug is vadastuximab talirine (SGN-CD33A) for the study.

**Serious AE (SAE):** is defined as an answer of “Yes” for the question “Was this Serious” in CRF form of “Adverse Events and Pre-Existing Conditions”.

**Time Since Initial Diagnosis:** is defined as

Date of first dose – date of initial MDS diagnosis + 1.

**Transformation to AML:** is defined as an answer of “Yes” for the question “Has the patient progressed to AML” in CRF form of “Follow-Up”.

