**Table 2: Kaplan-Meier Analysis Rules**

Situation	Date of Progression or Censoring	Outcome
No baseline and/or post-baseline disease assessment	Date of first dose	Censored
No documented progression	Date of last adequate response assessment (or Study Day 1 in the absence of a post-baseline response assessment)	Censored
PD documented during or between scheduled visits	Date of response assessment demonstrating PD	Event
New subsequent cancer therapy initiated prior to documented progression	Start date of new subsequent cancer therapy	Censored
Death before first PD assessment	Date of death	Event
Death between response assessment visits	Date of death	Event

For concomitant medication dates, see [Section 5](#) for imputation rules. For missing or partial start and stop adverse event dates, see [Appendix 4](#) for imputation rules.

Note that the actual value for date (not imputed) will be presented in all data listings and imputed dates will be used for derivations only.

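### PFS and DOR keep subjects transplanted in remission under follow-up for progression, but the assessment schedule and SAP Table 2 make no matching exception

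*Protocol*

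**What the plan says.** **Endpoint definitions.** For PFS and DOR, Protocol 13.6.4.2 sets a general rule: "Subjects who receive another anti-neoplastic therapy in the absence of documented progression will be censored at the time of receiving off-protocol therapy". It then qualifies that rule: "EXCEPT that subjects who receive stem cell transplant in remission will continue to be followed for progression". SAP Section 5 (PFS), 9.5.2.1 (DOR) and 9.5.2.2 (PFS) carry the same exception. Death from any cause is an event for both endpoints.

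**Assessment schedule.** Protocol 10.4 has post-treatment marrow samples taken "every 4 months through 24 months after EOT or until initiation of another anticancer treatment, progression, or relapse". Table 4 footnote r says "obtain every 4 months through 24 months after EOT or until initiation of another anticancer treatment, progression, or relapse". The synopsis, 9.1.1, 9.1.2, 9.4.3.1, 11.3 and SAP 3.1.1 and 3.1.2 carry the same stop. None mentions transplant. Figure 2 footnote b, in both documents, differs: disease assessment runs "every 4 months for 24 months or until disease progression", and new therapy is not named as a stop.

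**What continues after new therapy.** Protocol 10.4: "Subjects will be contacted for survival information and collection of subsequent anticancer treatment information approximately every 2 months until death or study completion". SOS/VOD is also followed for 100 days after certain transplants. The SAP's definition of AML transformation (Section 5) shows that the Follow-Up form asks "Has the patient progressed to AML".

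**Censoring table.** SAP 9.5.4 sends DOR and PFS to Table 2. Its row "New subsequent cancer therapy initiated prior to documented progression" censors at the start of that therapy, with no transplant exception.

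**The concern.** The endpoint text relies on information that the visit schedule does not clearly collect. Keeping a transplanted subject in the risk set is sound only if relapse after transplant can be seen. If it cannot, a subject who relapses and is alive at the cut-off is censored at the last assessment showing no progression, probably before transplant. One who relapses and dies becomes an event at death rather than at relapse. Events are then missed or dated late.

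SAP Table 2 adds a second conflict, because it gives the same subject a different outcome from SAP 9.5.2.1 and 9.5.2.2. Two programmers working from the same SAP could derive different PFS and DOR times. A relapse date that was never collected may also not be recoverable at analysis.

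**Working it through.** **1. Is transplant inside the stop rule?** The documents never say outright. The exception in 13.6.4.2 is carved out of a rule about other anti-neoplastic therapy, which implies that transplant is such a therapy. Protocol 9.5.3 bars allogeneic transplant during study treatment, so an allogeneic transplant falls in the post-treatment period that the stop wording governs.

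**2. What happens to a subject transplanted in remission?**

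| Text followed | Relapse after transplant, alive | Relapse after transplant, then death |
|---|---|---|
| PFS/DOR text with the 10.4 stop | Censored at last progression-free assessment, unless AML is reported | Event at death |
| PFS/DOR text with Figure 2 footnote b | Event at relapse, if within 24 months of assessment | Event at relapse |
| SAP Table 2, literal | Censored at start of new therapy | Censored at start of new therapy |

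The last row assumes that the new-therapy row takes precedence over the death rows; Table 2 states no order.

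**3. Does the AML question fill the gap?** Only in part. Appendix 18.6 counts return to the pretreatment blast percentage, a fall in counts or transfusion dependence as relapse. Eligibility requires at least 5% and under 20% marrow blasts, so a subject can return to pretreatment blasts and meet the relapse definition while still having MDS.

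**4. How many subjects?** The plan states no PFS or DOR figure. Its sample size supplies the scale: 106 subjects at 1:1 is 53 per arm. This reproduces with unpooled variance: SE = √[(0.30×0.70 + 0.55×0.45)/53] = 0.0929; 0.25/0.0929 − 1.645 = 1.046; power 85.2%, against the stated 85%. Expected responders are 53×0.55 = 29.2 and 53×0.30 = 15.9. The share transplanted in remission is not given; 5% to 30% is assumed.

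| Share of responders transplanted | Experimental | Comparator |
|---|---|---|
| 5% | 1.5 | 0.8 |
| 10% | 2.9 | 1.6 |
| 20% | 5.8 | 3.2 |
| 30% | 8.7 | 4.8 |

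**5. How large is the effect per transplanted subject, if only deaths were seen?** This is an illustration; every input is an outside assumption. Times are exponential, with median time to relapse 8 to 24 months (rate a = ln2/median), median 8 months from relapse to death (b = ln2/8 = 0.0866 per month), 15% per year death without relapse (n = −ln0.85/12 = 0.0135 per month) and T = 24 months of follow-up.

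- True events: 1 − exp[−(a+n)T]. Median 8: 1 − exp(−2.404) = 91%. Median 24: 1 − exp(−1.018) = 64%.
- Relapsed, alive and unrecorded at T: a[exp(−bT) − exp(−(a+n)T)]/(a+n−b). Median 8: 22%. Median 24: 15%.
- Recorded events, by subtraction before rounding: 69% and 48%.
- Recorded, but at death rather than relapse: a/(a+n) × true events − unrecorded = 56% and 28%.

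**6. Trial scale.** Multiplying steps 4 and 5, unrecorded relapses are about 1.46×0.154 = 0.2 to 8.75×0.222 = 1.9 in the experimental arm, and 0.80×0.154 = 0.1 to 4.77×0.222 = 1.1 in the comparator arm.

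**The case against.** The strongest reply is that this is ambiguity, not a gap. Protocol 9.5.3 lists allogeneic transplant separately from systemic anti-neoplastic therapy, and 10.4 sets transplant apart from additional therapy. The exception in 13.6.4.2 could therefore be read as a specific instruction that overrides the general stop. Protocol 9.4.3.1 also promises follow-up for disease status, Figure 2 footnote b has no new-therapy stop, and the Follow-Up form captures AML.

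Part of this stands. A reader might infer that post-transplant relapse is never recorded and that only deaths count. The documents do not support that: Figure 2 footnote b allows assessment to continue, AML can be reported, and under a literal Table 2 post-transplant deaths would not count either.

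It does not remove the conflict. The disease-status sentence in 9.4.3.1 refers to 10.4, which contains the stop. The body text of 9.1.2 includes the stop that its own figure footnote omits. A site that follows the visit schedule has no clear instruction to keep assessing these subjects.

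The reply on size also stands. Transplant candidates are excluded at screening, the SAP summarises PFS and DOR descriptively, and ORR is assessed only until EOT.

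**Conclusion.** The inconsistency holds. PFS and DOR are defined to need progression follow-up after transplant in remission; most schedule passages end it at a new anticancer treatment, one figure footnote does not, and SAP Table 2 censors at new therapy. Under the endpoint text, post-transplant events would come mainly from deaths, because relapse short of AML has no clearly scheduled assessment. Under Table 2 they would all be censored.

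The effect is limited to secondary endpoints and probably to a few subjects. On the assumed ranges, unrecorded relapses stay below 2 in the experimental arm and at about 1 or fewer in the comparator arm, with some further events dated late. If equal shares of responders were transplanted, the arm with more responders would carry more of the distortion. A reader might go on to infer a material bias in the PFS or DOR comparison. That is not shown: the transplant rate, relapse times and mortality are not in the documents, and no shift in either endpoint has been calculated. The case for acting is that the correction is cheap and makes both endpoints computable as defined.

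**What to change.** - **Stop wording.** Wherever it appears (Protocol synopsis, 9.1.1, 9.1.2, 9.4.3.1, 10.4, 11.3 and Table 4 footnote r; SAP 3.1.1 and 3.1.2), state that transplant in remission does not end progression follow-up for PFS and DOR. Bring Figure 2 footnote b into line.
- **Data collection.** For these subjects, record relapse or progression status and date, as documented in local care, at the existing 2-monthly contact. This adds no study procedure.
- **SAP Table 2.** Add the transplant exception to the new-therapy row, and allow the locally documented relapse date as the event date. The table now dates progression only by a response assessment, so it would not clearly admit that date.

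All three parts are needed; changing the schedule alone would leave Table 2 censoring the events. The cost is a sentence in each listed place, one or two Follow-Up form fields and a Table 2 edit. The drawback is that relapse dates from local care will be less regular than those from scheduled marrow examinations.
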